9.8 Efficacy Analyses

All efficacy analyses will be based on the FAS and all statistical tests will be 2-sided hypothesis tests performed at the 10% level of significance on those doses continued after the IA, accounting for the number of doses dropped at the IA. Also, all confidence intervals will be 2-sided confidence intervals, unless otherwise stated.

9.8.1 Primary Efficacy Endpoint

The primary endpoint is the binary response indicating (yes/no) whether a subject responded at Week 48 with a reduction of at least 2 points, without worsening of fibrosis, from baseline NAS.

The FAS will be used to assess the primary efficacy endpoint. The proportion of subjects at Week 48 with a reduction of at least 2 points without worsening of fibrosis from baseline NAS

will be analyzed. The difference between a volixibat dose and PBO will be tested with a stratified Cochran-Mantel-Haenzel test. The test will be stratified by presence or absence of T2DM at baseline and baseline NAS separated into two groups (NAS={4,5} or NAS={6,7,8}). Subjects with missing data for the primary efficacy endpoint at the Week 48 visit will be considered as non-responders. Holm multiplicity adjustment will be applied prior to determining statistical significance at the 0.1 level.

Analyses which explore the impact of the missing data on the primary efficacy endpoint will be conducted. These analyses may compare imputations of the missing values which favor the PBO and/or imputations which favor the active. In addition, analyses utilizing existing HFF and/or ALT data may be performed. Further, if the pattern of missing values does not appear uniformly distributed among the treatment arms, imputation method(s) based on informative missingness may also be performed. Analyses investigating the impact of missing data will be detailed in the Statistical Analysis Plan.

9.8.2 Secondary Efficacy Endpoints

Descriptive statistics will be presented for each time point at which the variable is measured (see **Table 1**) for the secondary efficacy endpoints. Binary secondary efficacy endpoints will be analyzed with the same method (stratified Cochran-Mantel-Haenzel test) as the primary efficacy endpoint. Continuous secondary efficacy endpoints will be analyzed with an ANCOVA model with change from baseline as the outcome variable; treatment group, presence or absence of T2DM at baseline, and baseline NAS separated into 2 groups (NAS={4,5} or NAS={6,7,8}) as factors and baseline values as a covariate. Endpoints include:

- Change from baseline to Week 48 on liver histology as measured by the individual NAS components (ballooning, inflammation, steatosis).
- Change from baseline to Week 48 on hepatic steatosis as measured by MRI-PDFF.
- Change from baseline to Week 48 on liver histology as measured by fibrosis stage. (NASH CRN)
- Resolution of NASH (defined as total absence of ballooning [score = 0], absent or mild inflammation [score 0-1], steatosis can be present [score 0-3]) without worsening of fibrosis as assessed by liver histology at Week 48.
- Change from baseline to Week 48 on serum liver-related biochemistry as measured by:
 - alanine aminotransferase (ALT)
 - aspartate aminotransferase (AST)
 - alkaline phosphatase (ALP)
 - gamma glutamyl transferase (GGT)
 - total bilirubin (TB)
- Change from baseline to Week 48 on metabolic indicators as measured by:
 - fasting serum glucose levels

- insulin levels
- HbA1c
- Change from baseline to Week 48 on serum lipids measured by:
 - fasting total cholesterol
 - HDL-C
 - LDL-C
 - triglycerides

9.8.3 Exploratory Efficacy Endpoints

Descriptive statistics will be presented for each time point at which the variable is measured (see [Table 1](#)) for the exploratory efficacy endpoints. Binary exploratory efficacy endpoints will be analyzed with the same method (stratified Cochran-Mantel-Haenzel test) as the primary efficacy endpoint. Continuous exploratory efficacy endpoints will be analyzed with an ANCOVA model with change from baseline as the outcome variable; treatment group, presence or absence of T2DM at baseline, and baseline NAS separated into 2 groups (NAS={4,5} or NAS={6,7,8}) as factors and baseline values as a covariate. Endpoints include:

- Change from baseline to Week 48 on liver histology as measured by the SAF scoring components: Steatosis (S), Activity (A), and Fibrosis (F)
- Change from baseline to Week 48 on anthropomorphic measures:
 - body weight
 - BMI
 - waist circumference
 - waist-hip ratio
- Change from baseline to Week 48 in subjects with T2DM on homeostasis measured by:
 - Homeostasis model assessment -IR (HOMA-IR)
 - HOMA-beta cell function (HOMA-%B)

9.9 Safety Analyses

The Safety Analysis Set will be used to assess the safety endpoints.

Adverse events will be coded using the Medical Dictionary for Regulatory Activities. Treatment-emergent AEs are defined as AEs that start or worsen on or after the date of the first dose of IP, and no later than the follow-up visit. The number of events, incidence, and percentage of TEAEs will be calculated by SOC, by preferred term, and by treatment group. Treatment-emergent AEs will be further summarized by severity and relationship to the IP. Adverse events related to the IP, AEs leading to withdrawal, SAEs, and deaths will be similarly summarized/listed.

Vital signs, ECG findings, and clinical laboratory tests will be summarized by treatment group and visit. Potentially clinically important findings will be summarized. Graphical presentation may be used when deemed necessary.

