4.5 Discontinuation of Subjects

A subject may withdraw from the study at any time for any reason without prejudice to their future medical care by the physician or at the institution. The investigator or sponsor may withdraw the subject at any time (eg, in the interest of subject safety). The investigator is encouraged to discuss withdrawal of a subject from the IP with the CRO Medical Monitor when possible.

If the IP is discontinued, regardless of the reason, the evaluations listed for both Visit 9/end of study (EOS) and Visit 10/Follow-up, are to be performed as completely as possible; however, the EOS liver biopsy will not be required for patients discontinuing prior to Week 44.

Comments (spontaneous or elicited) or complaints made by the subject must be recorded in the source documents. The reason for termination, date of stopping the IP, and the total amount of the IP taken must be recorded in the electronic case report form (eCRF) and source documents.

Subjects who discontinue will not be replaced.

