Subjects recruited into the study prior to the IA will continue with the same dosing regimen for the duration of the planned study participation. That is, a subject receiving a dose to which randomization is stopped after the IA will continue to receive that same dose throughout the course of the study, and complete all required assessments, unless a dose is determined to be unsafe, in which case the affected subjects would be discontinued from the study and followed as per Section 4.5. Subjects recruited into the study after completion of the IA will be randomized evenly to the remaining volixibat dose groups or PBO group by IRT. Thus, depending on the results from the IA, the study may be terminated, or one or two doses of volixibat may be discontinued. If the study is not terminated, subjects will receive a total of 48 weeks of IP.

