9.6 Sample Size Calculation and Power Considerations

These are the primary hypotheses that are being tested in this study:

- Null: The proportion of subjects at Week 48 with a reduction of at least 2 points without worsening of fibrosis from baseline NAS does not differ between any of the volixibat doses and PBO.
- Alternative: The proportion of subjects at Week 48 with a reduction of at least 2 points without worsening of fibrosis from baseline NAS does differ between at least one volixibat dose and PBO.

Response rates of 21% (PBO) and 45% (active) were reported in the FLINT trial ([Neuschwander-Tetri et al., 2015](#)) using the same primary end-point of reduction of NAS by at least two points (without worsening of fibrosis). Based on those response rates, 67 subjects per group completing the trial are needed for 80% power with a 10% type I error. Holm multiplicity adjustment was included in the sample size estimate.

Approximately 899 subjects will be screened to randomize 292 subjects to achieve 201 completers in the three arms (2 volixibat and 1 PBO) that continue after the IA (one dose is dropped at the IA); approximately 807 subjects will be screened to randomize 260 subjects to achieve 134 completers in the two arms (1 volixibat and 1 PBO) that continue after the IA (two

doses are dropped at the IA). After randomization of at least 80 subjects (20/treatment arm), a 24-week IA may eliminate at least one active dose group based on the criteria provided to the DMC. The sample size target for this study is 67 completers in each of the treatment groups that were not dropped at the IA (201 total if 3 arms continue, 134 if 2 arms continue). Accounting for a 20% dropout, 81 subjects will be randomized in each of the treatment groups that continue. Including the projected approximately 49 additional subjects randomized to a dose that is dropped at the IA, 292 subjects (81 for each arm that continues + 49 in the dropped arm) will be randomized if 3 arms (2 volixibat and 1 PBO) continue; 260 subject (81 for each arm that continues + 49 for each of the dropped arms) will be randomized if 2 arms (1 volixibat and 1 PBO) continue. Should the number of subjects randomized prior to the IA to a dose group that is dropped at the IA markedly deviate from the above projection, then the total number of subjects randomized will be adjusted accordingly, not to exceed approximately 324 subjects.

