9.7 Study Population

The Screened Set will consist of all subjects who have signed an informed consent.

The Randomized Set will consist of all subjects in the Screened Set who have been randomized into the study.

The Safety Analysis Set will consist of all subjects who take at least 1 dose of randomized IP, and have at least 1 post-baseline safety assessment (eg, coming back for any visit, reporting of an AE or reporting the absence of AEs).

The Full Analysis Set (FAS) will consist of all subjects in the Safety Analysis Set who have at least 1 post-baseline efficacy assessment (eg, MRI, liver biopsy, serum liver-related biochemistry measurement).

The Interim Analysis Set (IAS) will consist of all subjects in the Safety Analysis Set who have at least 1 post-baseline efficacy assessment (eg, MRI, ALT biochemistry measurement) on or before the Week 24 visit at the data cut time of the IA.

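### Section 9.9 summarises adverse events as crude percentages with no time at risk, so a dose stopped as unsafe, with about half of placebo's follow-up, has its steady-hazard events understated

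*Protocol*

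**What the plan says.** Section 9.9 names the measure: "The number of events, incidence, and percentage of TEAEs will be calculated by SOC, by preferred term, and by treatment group". Severity, relatedness, withdrawals, serious events and deaths are handled in the same way. The events counted are "AEs that start or worsen on or after the date of the first dose of IP, and no later than the follow-up visit", so the window closes sooner for a subject who leaves sooner. The denominator takes no account of length of follow-up: "The Safety Analysis Set will consist of all subjects who take at least 1 dose of randomized IP", with one post-baseline safety assessment as the only further condition (Section 9.7).

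Section 9.5.1 treats dropped doses in two ways. In general, subjects already on a dose that closes to randomisation stay on it to the end and have all their planned assessments. The exception is a dose judged unsafe, "in which case the affected subjects would be discontinued from the study and followed as per Section 4.5". Section 4.5 then provides one closing set of assessments: "the evaluations listed for both Visit 9/end of study (EOS) and Visit 10/Follow-up, are to be performed as completely as possible". Section 7.1.4 places the follow-up visit 4 weeks after the last dose. Placebo subjects who complete have 48 weeks of treatment plus those 4 weeks.

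**The concern.** A percentage of subjects with an event is comparable between groups only if the groups are watched for similar lengths of time. Here the protocol itself prescribes an outcome in which they are not. Only a finding of harm cuts follow-up for a whole arm, so the dose judged worst on safety has the least time in which further events can be recorded, and its percentages are pulled down most.

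The problem is length of follow-up, not calendar period. It remains if the stopped arm is compared with placebo subjects randomised on the same dates, because those placebo subjects go on to Week 52. At stake is the description of how harm varies with dose in a dose-finding trial whose first-listed secondary objective is safety and tolerability against placebo (Section 2.2.2).

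**Working it through.** **Inputs from the protocol.** Interim analysis after at least 80 subjects have 24 weeks of treatment (9.5.1). About 49 subjects in a dropped arm at that time, and 20% dropout: "Accounting for a 20% dropout, 81 subjects will be randomized in each of the treatment groups that continue" (9.6). Treatment 48 weeks, follow-up 4 weeks (7.1). The arm sizes are consistent with the plan's totals: 3 × 81 + 49 = 292 and 2 × 81 + 2 × 49 = 260. The protocol states no adverse event rate, so there is no stated figure to reproduce on the point itself.

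**Assumptions of this check.** Uniform accrual; exponential dropout reaching 20% at Week 48; a 52-week event risk of 30% on placebo with constant hazard; hazard ratio 2 at the unsafe dose. Lower risks are shown below.

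**Accrual.** With 4 × 49 = 196 randomised and 80 of them at 24 weeks or more, the other 116 entered in the last 24 weeks, a rate of 116/24 = 4.83 per week. Accrual has then run 196/4.83 = 40.6 weeks, and time since randomisation U is uniform on 0 to 40.6 weeks.

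**Time on drug.** Dropout hazard: −ln(0.80)/48 = 0.00465 per week, with dropout time D.
- Placebo: mean of min(D, 48) = 0.20/0.00465 = 43.0 weeks.
- Stopped dose: mean of min(D, U) = 19.1 weeks.

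Adding 4 weeks gives mean event windows of 47.0 and 23.1 weeks, a ratio of 0.49.

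**Crude percentage.** Event hazard λ = −ln(0.70)/52 = 0.00686 per week. The expected percentage is the mean of 1 − exp(−HR × λ × window). As a hand check at the mean windows, placebo is 1 − exp(−0.00686 × 47.0) = 27.6% and the doubled hazard is 1 − exp(−2 × 0.00686 × 23.1) = 27.2%. Averaging over the spread of windows gives:

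| 52-week risk | Placebo | Stopped dose, same hazard | Stopped dose, doubled hazard | Doubled hazard, not stopped |
|---|---|---|---|---|
| 30% | 27.3% | 14.4% | 26.2% | 46.8% |
| 10% | 9.1% | 4.5% | 8.8% | 17.3% |
| 5% | 4.5% | 2.2% | 4.4% | 8.8% |

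**Decision lag.** If subjects stay on the dose 8 weeks past the data cut and no new ones join it, mean time on drug is 26.2 weeks. At 30% risk the doubled hazard then shows 33.0%, against 27.3% on placebo.

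**Early events.** If half of the cumulative hazard falls in the first 4 weeks, placebo shows 28.6% and the stopped dose with doubled hazard 39.0%. If all of it falls in the first 12 weeks (placebo risk 20%), the stopped dose shows 33.9%, against 36.0% with full follow-up.

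**Person-time.** Under the constant hazard, events per 100 subject-years are 100 × 52 × 0.00686 = 35.7 on placebo and twice that, 71.3, at the stopped dose. The ratio of 2 is recovered whatever the truncation.

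**The case against.** The strongest reply is that this belongs to the SAP. Section 9.4 leaves methods for safety data and exposure to that document, and Section 9.9 excludes nothing. It also lists incidence next to percentage without defining it, so a rate per unit of time could be meant. That is fair as far as it goes. But Section 9.9 does choose a measure, and the percentage it names understates harm in a situation that Section 9.5.1 prescribes. If incidence means a rate, the text should say so.

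Several limits stand in full:
- The branch is narrow. Doses dropped as intolerable, futile or least promising keep their subjects to Week 48.
- Section 9.9 is descriptive and fixes no between-group test.
- The decision to stop a dose rests on the interim comparison, not on the final tables. For the event that prompted the stop, an excess has probably been seen already; the figures above do not condition on the stop and fit other events better.
- Laboratory tests, including the liver tests, are summarised by visit, and stool data by time point, so those are aligned in time. Open events are followed to closure.

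A reader might infer that a dose doubling a risk will look the same as placebo, or that the final tables will reverse the dose-harm relation. The documents do not support that as a general statement. Near-equality needs a roughly constant hazard and almost no decision lag, and Section 1.3 describes gastrointestinal events that lessened over treatment, which are among those least masked. A reader might also extend the point to unequal dropout with no dose stopped. The protocol plans a single 20% dropout; an assumed 10% against 40% at equal hazard gives only 29% against 24%.

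**Conclusion.** The point holds as a cheap improvement, confined to a dose judged unsafe at the interim analysis. That arm would have about half of placebo's follow-up for new events (23 against 47 weeks on average). For steady-hazard events with a 30% 52-week risk, a doubled hazard would show as about 26%, or 33% with an 8-week lag, where an arm left on treatment would show 47%; placebo shows 27%. For front-loaded events the excess remains visible at 39% against 29%. The relative understatement is similar at risks of 5% and 10%. The size rests on uniform accrual, the projected 49 per arm, 20% dropout, and the assumed risk, hazard shape and hazard ratio, none of which the protocol gives for adverse events.

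**What to change.** In Section 9.9:
- define incidence;
- add exposure-adjusted rates (events, or first events, per 100 subject-years at risk) by group;
- add cumulative incidence of first event by group, with each subject censored at the end of his or her own event window, for any treatment-emergent event, serious events, and the gastrointestinal and liver groupings;
- state that a dose stopped as unsafe is compared with placebo only over the weeks its follow-up covers;
- keep the crude percentages as supportive tables.

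The cost is a few more tables from event and dosing dates already collected, with no extra subjects or visits and no change to how subjects are managed. The new estimates assume uninformative censoring. That holds only approximately for voluntary dropouts, and also for an arm stopped on its own safety data, where the censoring is not purely administrative; the report should say so. Rates per subject-year also average over time, so for early events the cumulative incidence over the shared weeks is the better guide.

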The IA will be conducted by an independent DMC after at least 80 subjects have received 24 weeks of treatment. The IA will evaluate the safety, tolerability and efficacy of 3 doses of volixibat each compared to PBO.

Once decisions as to dose elimination are made, additional sites may be added. Subjects recruited into the study prior to the IA will continue with the same dosing regimen for the duration of the planned study participation. Subjects recruited into the study after completion of the IA will be randomized evenly to the remaining dose groups (noted by “[1 or 2]... Dose TBD” in [Figure 1](#)) or PBO group by IRT. Thus, depending on the results from the IA, the study may be terminated, or one or more doses of volixibat may be discontinued. If the study is not terminated, subjects will receive a total of 48 weeks of investigational product (IP).

The study will be conducted over 3 periods: screening (10 weeks), treatment (48 weeks), and follow-up (4 weeks), with an IA at 24 weeks as outlined in [Figure 1](#).

Figure 1 Study Design Flow Chart

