6.2.2 Allocation of Subjects to Treatment

This is a double-blind, PBO-controlled study. The actual treatment given to individual subjects is determined by a randomization schedule.

Subject numbers are assigned to all subjects as they consent to take part in the study. Within each site (numbered uniquely within a protocol), the subject number is assigned to subjects according to the sequence of presentation for study participation.

The randomization number represents a unique number corresponding to the IP allocated to the subject, once eligibility has been determined.

Individual subject treatment is automatically assigned by the IRT.

Once a randomization number/unique identifier has been assigned, that number must not be used again if, for example, a subject is withdrawn from the study. If a randomization number/unique identifier is allocated incorrectly, the clinical research associate (CRA)/study monitor must be notified as soon as the error is discovered.

IP packaging identification numbers, separate from randomization numbers/unique identifiers, may also be assigned to subjects for specific treatment assignment as dictated by the study. In these cases, the same IP packing identification number may not be assigned to more than 1 subject.

Subjects will be equally allocated to all volixibat doses and PBO if their randomization precedes the 24 week IA. If a subject's randomization occurs after the 24 week IA, subjects will be equally allocated to all remaining volixibat doses (determined based on the results of the IA) and PBO. The randomization will be stratified by baseline T2DM and NAS ≥ 6 or NAS = {4,5}. Subjects with fibrosis stages F0 through F3 may be enrolled, but the number of F0 subjects will be capped at 88 if 1 dose is dropped after the IA and at 78 if 2 doses are dropped (approximately 30% of the total number of subjects randomized).

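### If a dose is dropped at the interim analysis, the final descriptive tables set it beside a placebo group of which about 40% (projected) was randomised after that dose closed; a supplementary concurrent display would help.

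*Protocol*

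**What the plan says.** All references are to the protocol.

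- **Allocation.** Sections 3.1 and 6.2.2 give equal allocation to 5, 10 and 20 mg and placebo before the IA. Afterwards, "subjects will be equally allocated to all remaining volixibat doses" and placebo, with nobody new on a dropped dose. Section 3.1 adds: "Once decisions as to dose elimination are made, additional sites may be added".
- **Numbers.** Section 9.6: "Accounting for a 20% dropout, 81 subjects will be randomized in each of the treatment groups that continue". A dropped dose is covered by the words "Including the projected approximately 49 additional subjects randomized to a dose that is dropped at the IA", giving the total "292 subjects (81 for each arm that continues + 49 in the dropped arm) will be randomized" when three arms continue.
- **Dropped-dose subjects stay in.** Section 9.5.1 keeps them on their assigned dose with all assessments, unless the dose is judged unsafe. They therefore appear in the final tables.
- **Displays.** Section 9.7 defines the Safety Analysis Set as treated subjects with a post-baseline safety assessment, without regard to when they were randomised. Section 9.9: "The number of events, incidence, and percentage of TEAEs will be calculated by SOC, by preferred term, and by treatment group". It treats vital signs, ECGs and laboratory tests in the same way, by group and visit. Section 9.10.2 describes stool data by treatment group. For the secondary efficacy endpoints, section 9.8.2 says "Descriptive statistics will be presented for each time point at which the variable is measured".
- **Existing limit.** Section 9.8 restricts efficacy hypothesis tests to doses continued after the IA. Sections 9.9 and 9.10.2 have no counterpart for the descriptive summaries.

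**The concern.** While a dose is open, its subjects and the placebo subjects are randomised side by side, so differences between them are protected by randomisation. Once the dose closes, new placebo subjects have no counterpart on it. Pooling all placebo subjects into one column then compares an arm from one recruitment period with an arm from two. The same holds for a dropped dose set beside a retained dose.

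This matters only if the periods differ, and the protocol gives reasons why they might. Sites may be added after the IA. Amendment 3 (March 2017, against a planned start of July 2016) admitted F0 subjects and raised the AST/ALT and HbA1c limits, so anyone enrolled under the narrower criteria belongs to the earlier period. The F0 cap is cumulative and depends on the IA outcome, so the F0 share may also differ between periods. None of this is an error in the plan; it shows only that a shift in case mix is possible.

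Safety and tolerability against placebo is a stated secondary objective of a dose-finding trial. A dose dropped for harm, intolerance or futility is one whose final columns will be read closely. A change over time in event reporting, case mix or sites could look like a dose effect or hide one.

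**Working it through.** **Inputs.** From section 9.6: 81 randomised per continuing arm, about 49 on a dropped dose, totals of 292 and 260, and a ceiling of about 324. From sections 3.1 and 6.2.2: equal allocation before the IA, so placebo also holds about 49 at that point. The protocol gives no figure for a shift between periods, so the shifts and event rates below are assumptions.

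**1. Reproduce the plan's totals.**
- One dose dropped: 3 × 81 + 49 = 292, as stated.
- Two doses dropped: 2 × 81 + 2 × 49 = 260, as stated.
- Ceiling: 4 × 81 = 324, as stated.

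**2. Non-concurrent share of placebo.** w = (81 − 49)/81 = 32/81 = 39.5%, whether one or two doses are dropped. Each retained dose has the same share.

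**3. Dependence on the projected 49.**

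| Per arm before the IA | Share randomised afterwards |
|---|---|
| 20 | 75% |
| 40 | 51% |
| 49 (projection) | 40% |
| 60 | 26% |
| 81 (total 324) | 0% |

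**4. Bias from a shift.** Suppose the drug has no effect, an event has incidence p before the IA and p + D after it. The dropped dose shows p. The full placebo column shows (1 − w)p + w(p + D) = p + wD. The apparent difference, dropped dose minus placebo, is −wD.
- D = 10 points: 0.395 × 10 = about 4 points.
- D = 20 points: 0.395 × 20 = about 8 points.

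A retained dose and placebo each have 49 + 32 subjects, so the shift cancels between them.

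**5. Precision given up by a concurrent display.** SE of a risk difference, equal incidence in both arms:
- At 50%, 49 v 81: √[0.25 × (1/49 + 1/81)] = 9.0 points. For 49 v 49: √[0.25 × 2/49] = 10.1 points.
- At 20%, 49 v 81: √[0.16 × (1/49 + 1/81)] = 7.2 points. For 49 v 49: √[0.16 × 2/49] = 8.1 points.

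**6. Bias and precision together, at 50% incidence.** With D = 10 points, the full placebo column has root mean squared error √(3.95² + 9.05²) = 9.9 points, against 10.1 for the concurrent comparison. They break even where wD = √(10.10² − 9.05²) = 4.5 points, that is D = 4.5/0.395, about 11.4 points.

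**The case against.** The strongest reply is that section 9.9 is ordinary protocol wording and section 9.4 leaves methods to the SAP, which could add a split by period. The protocol nowhere says in words that a dropped dose will be judged against all 81 placebo subjects. That stands as a limit on the point: the full placebo column follows from the Safety Analysis Set definition and the by-group display, not from an explicit instruction.

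Second, the comparison on which a dose is dropped is already concurrent. Section 9.5.1 compares each dose with placebo at the IA on safety, tolerability and efficacy, and section 9.5.2 adds regular committee review. Section 9.8 keeps dropped doses out of the formal efficacy tests. All of this stands. A reader might infer that the primary analysis, or a retained dose against placebo, is biased by the dose drop. The documents do not support that, because those arms recruit equally in both periods.

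Third, a reader might infer that every dropped-dose statement should rest on the concurrent subset alone. Step 6 does not support that. At a 10-point shift the full placebo column is marginally the more accurate, and discarding 32 placebo subjects is unhelpful for uncommon events. This argues for a supplement rather than a replacement.

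Finally, if a dose is judged unsafe, its subjects are discontinued and their exposure is cut short. A concurrent table does not correct that.

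**Conclusion.** The point holds as a modest one about reading descriptive tables. If a dose is dropped and the projection of 49 is about right, 40% of the placebo column and of each retained-dose column is non-concurrent with it. Contrasts with the dropped dose then carry a bias of about 0.4 times any shift between periods. It would be too strong to say that dose-related harm will be confounded with period. A drop is only possible, 49 is a projection, new sites are only permitted, and no shift is documented. The 4- and 8-point figures illustrate assumed shifts of 10 and 20 points.

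The case is clearest for the safety and stool summaries, which are specified by treatment group. It is weaker for descriptive efficacy, where section 9.8.2 does not mention dropped doses. No formal test is affected. This is a cheap improvement, not a flaw that threatens the trial's conclusions.

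**What to change.** Add one sentence to sections 9.9 and 9.10.2 and to the descriptive part of section 9.8.2, with these elements:

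- For any dose dropped at the IA, the key tables are also shown as a supplement restricted to subjects in all arms randomised before the IA decision was implemented.
- The full-group tables are kept and remain the main display for retained doses.
- Statements about a dropped dose, against placebo or across doses, are checked against the concurrent display, and any material disagreement is reported.

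The date on which the randomisation system stopped assigning the dose defines the cohort, so no new data are needed. The cost is a repeat of the key tables, with somewhat wider intervals in the supplement (at 50% incidence, an SE of 10.1 instead of 9.0 points). If no dose is dropped, the provision is not triggered.
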